2.3 Potential Risks and Benefits

2.3.1 Potential Risks

2.3.1.1 Overview

The majority of transplant centers in the United States are currently routinely using valganciclovir or intravenous ganciclovir for prevention of CMV infection and disease in liver transplant recipients, either as primary antiviral prophylaxis or in a preemptive therapy strategy (10). Similarly, acyclovir at HSV suppressive doses is routinely used for the prevention of HSV reactivation for the first month post-transplant in patients who are not receiving CMV prophylaxis, and is a grade I recommendation in the American Society of Transplantation SOT ID Guidelines (53). The current study proposes to use these same antiviral drugs that are already in routine use in the majority of liver transplant centers. The present study will systematically compare two different strategies using the same antiviral drugs that are already

routinely used at US liver transplant centers. As a result, the potential risks of the antiviral medications for study subjects in the present study are deemed to not be different than in standard clinical practice. Similarly, since both CMV prevention strategies (prophylaxis and preemptive therapy) are currently used in clinical practice in US and European liver transplant centers, there is no anticipated increased risk to study participants of randomization to one or another strategy. The potential toxicities/side-effects of each of these agents are provided in the subsequent sections.

2.3.1.2 Ganciclovir

Valganciclovir when taken by mouth is rapidly converted in the body to its active form, ganciclovir. It is estimated that tens of thousands of persons have received either intravenous or oral formulation ganciclovir over the last 22 years since its initial approval. Based on its efficacy and general tolerability, ganciclovir is currently recommended as a first-line agent for prevention and treatment of CMV infection and disease in HIV, solid-organ transplant, and hematopoietic cell transplant (HCT) populations (49, 54). See the package insert for more information. Ganciclovir is generally well-tolerated. The most common adverse effects, which appear to be related to longer durations of exposure and use of concomitant drugs with similar toxicities, are various hematological adverse effects, most commonly leukopenia and neutropenia which are reversible after drug discontinuation. The potential toxicities of ganciclovir have been extensively studied *in vitro*, *in vivo*, and in placebo-controlled studies in humans. Based on animal and cell culture data, ganciclovir is considered a potential human carcinogen, teratogen, and mutagen. It is also considered likely to cause inhibition of spermatogenesis. No human data exist that estimate the actual risk of these effects. Thus, it is used judiciously and handled as a cytotoxic drug in the clinical setting.

2.3.1.2.1.1. Hematologic toxicity

Neutropenia is the principal toxicity of ganciclovir and valganciclovir. The incidence is highest in HCT recipients and HIV-infected individuals, followed by pediatric patients with congenital CMV disease and organ transplant recipients. Many studies have demonstrated the effect occurs late after drug administration (9,55, 56). In fact several studies in HCT recipients, the most susceptible population for this complication, show that the median time of onset is 5 weeks after start of drug administration. Neutropenia was documented in 8.2% of the patients who received 100 days of valganciclovir in the PV-16000 study however discontinuation of the drug was required in only 2% (9). Another recent randomized trial of valganciclovir vs. ganciclovir at treatment doses (900 mg twice daily and 5 mg/kg twice daily, respectively) for CMV disease in SOT recipients showed a neutropenia rate of 1.2% and 0%, respectively, at 21 days of treatment (57). Ganciclovir-related neutropenia is reversible (9, 55, 57). The time to recovery can be hastened by administration of G-CSF (54).

Most placebo-controlled randomized studies, including those in stem cell transplant patients, do not show a difference in the incidence of thrombocytopenia and platelet transfusion requirements (8, 9, 57-60). However, there are rare anecdotal reports of ganciclovir-related pancytopenia. One study of ganciclovir prophylaxis in HCT recipients reported delayed platelet engraftment (61). Overall, the potential to cause thrombocytopenia is considered low.

A trend towards anemia has been shown to occur in HIV-infected patients treated with valganciclovir. However, no strong evidence exists in transplant recipients and other patient populations, suggesting that the effect may be related to concomitant medications specific to the HIV setting. One recently completed phase III randomized trial of prolonged valganciclovir prophylaxis in HCT recipients, a population that would be considered at particularly high risk for this complication, did not show an increased rate of anemia or red blood cell transfusion requirements (62). Other recent randomized trials also did not show an increased risk of anemia (9, 63).

Key studies summarizing the incidence of neutropenia with valganciclovir use in organ transplant recipients are shown below.

Reference	Incidence of neutropenia (n/n)	Discontinuation of valganciclovir
(64)	4% (2/47)	2 (resolved in both)
(9)	8.2%	2%
(57)	1.2% (2/164)	Not known
(65)	4% (2/49)	0%
(66)	5.7% (4/70)	0%
(2)	15% (25/164)	<1%

2.3.1.2.2 Renal toxicity

Results from randomized trials do not support a role for ganciclovir or valganciclovir as causes of renal toxicity. None of the recently conducted randomized trials shows an increased risk of renal toxicity (62, 63), however, two earlier trials, one in heart transplant recipients with IV ganciclovir (67, 68) showed increased rates of renal insufficiency. While the potential to cause direct toxicity appears to be low, we will monitor renal function closely and adjust doses based on creatinine clearance according to the package insert.

2.3.1.2.3 Neurotoxicity

This is rarely observed and is not statistically significant between study arms of most randomized trial except one study in HCT recipients (63). This effect probably occurs only in a setting of concomitant drugs with neurotoxic potential and high blood levels of ganciclovir in the setting of renal insufficiency.

2.3.1.2.4 Carcinogenicity

Ganciclovir and valganciclovir are considered potential human carcinogens (see package insert). No studies have been performed to systematically assess this potential in humans. Although tens of thousands of transplant and HIV infected patients have been treated

with ganciclovir over the past ~20 years, no reports of an increased risk of cancer have been published. However, this does not rule out possible carcinogenic effect.

2.3.1.2.5 Teratogenicity

There are potential reports of ganciclovir-associated teratogenicity in laboratory animals but not in humans. Nevertheless, this drug is contraindicated in patients who are or are planning to become pregnant. For the purposes of this study, all subjects will be screened and excluded for pregnancy/possible pregnancy. For the three months following receipt of ganciclovir, abstinence or an effective method of birth control for both partners is recommended.

2.3.1.2.6 Summary of human toxicity data

Ganciclovir-related neutropenia occurs very uncommonly in persons without underlying bone marrow dysfunction and generally occurs at a median of 5 weeks after drug exposure. In patients without underlying bone marrow dysfunction, two recent trials showed very low rates of neutropenia after 3-4 weeks of ganciclovir at doses similar to those proposed in this protocol (2% within first 4 weeks with prophylaxis of 900 mg VGCV/day (9); 1.2% at day 21 with 900 mg valganciclovir twice daily; 0% at day 21 with 5 mg/kg ganciclovir twice daily (57). There is no convincing evidence that ganciclovir or valganciclovir cause thrombocytopenia.

Anemia has been observed in HIV-infected subjects, but there is no evidence that it is a problem in transplant patients or in the treatment of congenital disease. There may be some risk of renal toxicity, however, this was not consistently observed across randomized trials. Other potential safety issues include teratogenicity and carcinogenicity.

Summary of ganciclovir and valganciclovir toxicities		
Adverse effect	Human data	Documented in randomized trials
Neutropenia	Yes	Yes
Thrombocytopenia	Yes	No
Anemia	Yes	Some (HIV only)
Renal dysfunction	Yes	No (none in recent trials)
Gastrointestinal effects	Yes	Yes
Tumors	No	No
Birth Defects	No	No

Data in Table summarized from references 9, 55-63

2.3.2 Other risks

2.3.2.1 Blood draws

Bruising, soreness, anemia, or very rarely, infection, may occur as a result of venipuncture used to obtain blood from the participant's vein. The participant may feel lightheaded when the blood is drawn. Every attempt will be made to coordinate research blood draws with clinical blood draws to avoid extra needle sticks. The schedule of blood draws needed for the study are very similar to the schedule of blood draws that are considered standard of care post liver transplant. Only at time points at which blood is not being drawn for clinical purposes but needed for study purposes will a separate venipuncture be performed. Approximately 312 ml (~20 tablespoons) of blood will be collected specifically for study purposes over the 12 months of study participation in the preemptive therapy group and 172 ml (~11 tablespoons) in prophylaxis group. This total blood volume over the study period is well within accepted limits of blood draw.

2.3.2.2 Invasion of privacy

Personal Health information is to be collected about study participants during this study. There is a theoretical risk (as for any research study) that the participant's privacy may be breached. Study staff will take numerous precautions to protect participant privacy. Only authorized study personnel will access medical records and only specific clinical and laboratory information will be extracted from the medical record. Study codes (rather than subject identifiable information) will be used for all data collection documents. All study specimens will be de-identified and marked with only study codes before being sent to the central study laboratory. All study personnel have been appropriately trained regarding subject privacy and HIPAA regulations. Confidentiality of subject information will be strictly observed, and final publication of results will not include any subject identifiable information.

2.3.3 Potential benefits

There are no known direct benefits to study participants. All study participants will be followed more closely than is typically done during the course of routine clinical care. As a result, it is possible that some medical problems (specifically CMV disease) might be detected earlier for study participants than would have been the case if they had not been in the study.

3 OBJECTIVES

3.1 Study Objectives

3.1.1 Primary objective

The primary objective is to compare prophylaxis versus preemptive therapy using valganciclovir for the prevention of CMV disease in R-/D+ liver transplant recipients

3.1.2 Secondary objectives

To assess the two preventive strategies for:

- Clinical outcomes (major bacterial, fungal and non-CMV viral infections, rejection, graft loss and mortality) at one year post transplantation.
- Hematologic toxicity (assessment of neutropenia and receipt of hematopoietic growth factor during study days 1-107)

3.1.3 Exploratory objectives

To assess the two preventive strategies for:

- The development of CMV-specific immunity following transplantation
- Cost effectiveness of the regimens
- Differences in clinical outcomes (mortality, OI, malignancies, and the need for renal replacement therapy) at 1 to 7 years post transplantation.

3.2 Study Outcome Measures

3.2.1 Primary outcome measure

The primary outcome measure is the incidence of CMV disease by 12 months post-transplant.

3.2.2 Secondary outcome measures (compared between 2 groups)

1. Clinical outcomes within 12 months post-transplant
 - Incidence of late-onset CMV disease (CMV disease occurring after 100 days post-randomization)
 - Incidence of major bacterial, fungal, and non-CMV viral infections
 - Incidence of allograft rejection
 - Incidence of graft loss (retransplantation)

- All-cause mortality
- 2. Hematologic toxicity (assessed until 107 days post-enrollment)
 - Incidence of neutropenia (ANC <1,000 and <500/ μ L)
 - Hematopoietic growth factor (granulocyte colony stimulating factor) for neutropenia - (receipt of hematopoietic growth factor during study days 1-107)

3.2.3 Exploratory end-points (compared between 2 groups)

- 1. Clinical outcomes
 - Time to onset of CMV disease (disease free survival) through 12 months post-transplant
 - All-cause mortality, rejection episodes, graft loss and retransplantation, opportunistic infections, need for dialysis, and post-transplant malignancies will be assessed until study closure (7 years from enrollment maximum).
- 2. Immunologic endpoints:
 - CMV-specific immunity at 100 days, 6 and 12 months post-transplant
 - a. CMV-specific T-cell responses
 - b. CMV-specific neutralizing antibody responses
- 3. Cost effectiveness of the 2 approaches:
 - Total costs for each regimen
 - Cost utility analysis (cost per quality adjusted life-years)

4. STUDY DESIGN

This is a /prospective, randomized, multicenter trial of prophylaxis versus preemptive therapy for the prevention of CMV disease in R-/D+ liver transplant subjects. Subjects meeting study criteria and who have provided informed consent will be randomized within 10 days post-transplant to receive, in an open label design, either prophylaxis with valganciclovir 900 mg once daily for 100 days or preemptive therapy (weekly monitoring for CMV viremia by plasma PCR weekly for 100 days post-randomization with initiation of valganciclovir 900 mg twice daily at onset of CMV viremia and continued until plasma PCR is negative on two consecutive weekly PCR tests). All dosages will be adjusted for renal dysfunction. Subjects will be followed during the intervention period (100 days post randomization) and until 12 months post-transplant for CMV disease, toxicity, and clinical outcomes (opportunistic infections, rejection, graft loss, retransplantation and mortality).

All-cause mortality, rejection episodes, graft loss and retransplantation, opportunistic infections (bacterial, fungal), need for dialysis, and post-transplant malignancies will be assessed until study closure (7 years from enrollment maximum).

Additionally, the impact of the two CMV prevention strategies on CMV-specific cellular and humoral immune responses will be evaluated at 100 days after randomization, and 6 and 12 months post-transplant.

It is anticipated that ~20-22% of all liver transplant recipients will belong to the R-/D+ group and will qualify for the study. Approximate time to enrollment will be 3.5 years. A minimum of 176 subjects will be enrolled in the study. Allowing for over-enrollment to replace dropouts, up to 205 subjects may be enrolled to achieve the target enrollment of 176 (see section 5.4.3.3). There will be a single interim analysis for the primary endpoint of CMV disease as adjudicated by an independent End Points Committee. This analysis will be conducted after~ 60 subjects have been enrolled and followed for 1 year. Study closure will occur 2 years after the enrollment of the last subject.

5. STUDY POPULATION

Male and female liver transplant patients of any ethnicity are eligible for screening and enrollment.

5.1 Recruitment Strategies

Site investigators are all clinicians and also care providers for the liver transplant recipients at their respective institutions and therefore have direct access to the study population. The study population will be drawn from in hospital setting. Potential subjects will be identified by the site investigators and the study coordinators. Although the subjects may return to their hometown, which may be remote from the transplant center, close and longitudinal follow up of patients is a standard of care at all transplant centers.

5.2 Subject Inclusion Criteria

Subject must:

1. Be \geq 18 years of age
2. Have negative CMV serology (confirmed within 6 months of transplant) and receive a liver from a donor with positive CMV serology (R-/D+)
3. Have received their first orthotopic liver transplant (the transplanted liver may be deceased donor or live donor graft) within 10 days prior.
4. Have absolute neutrophil count $> 1000/\mu\text{L}$ at randomization
5. If female, and not postmenopausal or surgically sterile, must have negative pregnancy test (serum or urine) within 48 hours prior to randomization and must also agree to use medically approved method of contraception. Acceptable methods include: barrier method, intrauterine device (hormonal or non-hormonal), oral hormonal contraceptives, abstinence for 100 days after randomization and 3 months after valganciclovir cessation. If male, and has not had a vasectomy, he must agree to practice barrier method of contraception for 100 days after randomization and 3 months after valganciclovir cessation
6. Subject or legally authorized representative has provided written informed consent.

5.3 Subject Exclusion Criteria

Subject must not:

1. Be currently enrolled in any interventional trial of an investigational therapeutic agent unless co-enrollment has been approved by study PIs and the DMID prior to enrollment

2. Have hypersensitivity to acyclovir, ganciclovir or valganciclovir
3. Be breast-feeding mother
4. Have known HIV infection (based on testing performed during the transplant evaluation process).
5. Be undergoing multi organ transplant or have undergone prior organ transplant
6. Have expected life expectancy of less than 72 hours.

5.4 Study Procedures

5.4.1 Screening

Potential subjects will be identified via assessment of medical record information using IRB-approved procedures. Since the investigating physician at all sites is both the caregiver and investigator, IRB-approved waiver [addressing Federal Policy criteria (45CFR 46.116(d)] for the screening portion of the consent will be obtained to access the medical record to identify potential research subjects. Medical records during screening will be reviewed for the limited purpose of determining potential eligibility of the subjects for the study. Eligible subjects will then be approached for informed consent. All subjects will provide an informed consent prior to enrollment in the study.

After appropriate informed consent has been obtained and before randomization of the subject, the following clinical laboratory tests as defined in the inclusion and exclusion criteria will be performed:

- In women of child bearing potential only: pregnancy test (serum or urine) - the results of this must be negative before proceeding. Pregnancy testing completed as SOC with-in 48 hours of randomization is acceptable.
- CMV serology (if not performed within 6 months of the transplant), absolute neutrophil count and serum creatinine level. These tests are performed as standard of care and are not study specific evaluations.

5.4.2 Randomization

Subjects will be randomized in 1:1 allocation to one of 2 study groups. All subjects that have met all criteria for study enrollment and have given written informed consent will be randomized via a web-based randomization system at the study web-portal.

The study team member randomizing the subject will get an immediate message providing group assignment. Randomization at each site will be stratified by: 1) the receipt of lymphocyte depleting induction and 2) dialysis at time of randomization. Randomization will occur as soon as it is feasible, but no later than 10 days after transplantation. Inadvertently randomized

subjects who do not meet the inclusion/exclusion criteria or those who are withdrawn prior to receiving the study drug will be replaced.

Subjects receiving lymphocyte depleting induction at the time of transplantation (even for those randomized to the preemptive therapy group) may receive up to 10 days of antiviral therapy with valganciclovir or IV ganciclovir after transplantation. Additionally, if the treating physician prescribes valganciclovir or IV ganciclovir for any length of time prior to randomization, it will not preclude subject enrollment. For subjects assigned to the prophylaxis group, the first dose of study drug should be given on the day of randomization regardless of lymphocyte induction. For subjects in the preemptive group that have received lymphocyte depleting induction, antiviral therapy with valganciclovir or IV ganciclovir will be given for ten days then stopped. Subjects that have not received lymphocyte depleting induction, but have received doses of valganciclovir or IV ganciclovir after transplantation prior to randomization, will have the pre-randomization treatment stopped and begin study treatment on randomization day based on their assigned group.

5.4.3 Discontinuation from Study and Withdrawal

5.4.3.1 Discontinuation from study

Under certain circumstances, an individual subject may be terminated from participation in this study. The site investigator must discuss potential subject discontinuation with the study PIs as soon as possible. Specific events that will result in discontinuation include:

- Site investigator decides to terminate participation for reasons of subject safety or to prevent compromising the scientific integrity of the study
- New scientific developments indicate that the treatment is not in the subject's best interest
- Subject was inappropriately enrolled based on inclusion/exclusion criteria
- Subject undergoes retransplantation after 30 days after randomization (please see section 6.2.5 for rationale)
- Study is terminated

For subjects who have received study product and discontinue from the study for any of the aforementioned reasons, every effort will be made to complete the safety specific evaluations.

5.4.3.2 Withdrawal

A subject may be withdrawn from study for the following reasons:

- Subject refuses further participation (consent withdrawn)
- Inappropriate enrollment (subject did not meet the inclusion criteria or met the exclusion criteria)

The date of last contact with the subject and the reason for withdrawal will be recorded in the CRF.

5.4.3.3 Handling of discontinuations and withdrawals

Should a subject discontinue prematurely, follow up assessments will be conducted per protocol. If the reason for removal of a subject from the study is an AE, specific event or test will be recorded on the CRF and follow up assessments will be continued. The exception to this would be if consent is fully withdrawn to any further collection of data. In the event that a subject discontinues participation after randomization but prior to receiving study drug or the subject was inappropriately enrolled, the subject will be replaced. No additional procedures or follow-up will be performed on subjects who discontinue prior to receiving study drug.

For subjects who withdraw consent from the study prior to receiving study product, there will be no further collection of data or study specific procedures. For a subject that has received study product then withdraws consent, the subject will not be required, but will be encouraged to complete safety specific evaluations.

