6 STUDY INTERVENTION/INVESTIGATIONAL PRODUCT

6.1 Study Product Acquisition/Description

Valganciclovir is the standard of care for CMV prevention at all participating centers. Valganciclovir will be used on an open-label clinical basis and billed to the subject and/or insurer. The subjects may fill prescription at any pharmacy per standard clinical care at that institution. No medication will be provided specifically for study purposes.

Valcyte ® (valganciclovir HCl tablets) is available as 450 mg pink convex oval tablets with "VGC" on one side and "450" on the other side. Each tablet contains valganciclovir HCl equivalent to 450 mg valganciclovir. The dispensing of valganciclovir will be according to manufacturer recommendations and routine institutional practices at the transplant center.

It is possible that a generic formulation of valganciclovir might be approved and become available during the study period. Investigators may use either formulation of valganciclovir (brand vs. generic equivalent) for study subjects at the protocol-described doses according to institutional standards. Because of the uncertainty of if/when generic valganciclovir might become available; it will not be possible to specifically control for this variable in the pre-defined analytic plan. However, we will include post-hoc analyses to assess the potential impact of generic formulations of valganciclovir on the study safety and efficacy endpoints.

For this protocol, all references to "study drug" are referring to valganciclovir when prescribed per Section 6.2, and beginning with Study Day 1. "Study drug" includes dose adjustment when indicated and the use of ganciclovir when indicated per clinical care.

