7.7.1 Study day 1-100

Drug administration phase

Prophylaxis therapy group will begin to receive antiviral prophylaxis treatment on day 1 and will continue receiving a daily dose through day 100. Please see protocol section 6.2 for a complete description and instructions regarding of prophylaxis dosing.

Preemptive treatment group will begin preemptive antiviral drug therapy during study days 1-100 only when viremia is detected by weekly surveillance and will continue preemptive therapy until two consecutive weekly CMV PCRs are negative. Therapy may be repeated if further detection of viremia is detected during the 100 day period.

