7.9 Therapy Discontinuation

Should a study subject's therapy be discontinued prematurely for any reason and consent has not been withdrawn, all clinical and laboratory evaluations will continue. Safety labs will be collected 1 week post last dose of therapy discontinuation. All key endpoints will be evaluated and all randomized study subjects will continue to be followed as long as possible and included in the final analysis.

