12.3.1 Intent-to-treat (ITT) population

All subjects who meet all eligibility criteria, sign an informed consent form, and are randomized to one of the treatment groups constitute the ITT population regardless of whether they received valganciclovir or had any post-baseline evaluations.

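### Section 5.4.3.3 stops following subjects who discontinue before study drug, a rule that falls mainly on the preemptive arm; 12.5.5 also attaches the valganciclovir criterion to the wrong arm, and the AE window for never-treated subjects needs stating

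*Combined protocol and SAP*

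**What the plan says.** **Follow-up.** The first paragraph of 5.4.3.3 opens with a general rule: "Should a subject discontinue prematurely, follow up assessments will be conducted per protocol". It names one exception, full withdrawal of consent to data collection. The same paragraph closes with "No additional procedures or follow-up will be performed on subjects who discontinue prior to receiving study drug". Section 5.4.2 adds that "those who are withdrawn prior to receiving the study drug will be replaced". Section 7.9, on stopping therapy early, ends by saying that "all randomized study subjects will continue to be followed as long as possible and included in the final analysis".

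**Study drug.** Under 6.1, references to study drug "are referring to valganciclovir when prescribed per Section 6.2, and beginning with Study Day 1", with ganciclovir included when clinically indicated. Prophylaxis subjects receive it on the day of randomization (6.2.2.1). Preemptive subjects begin it "only when viremia is detected by weekly surveillance" (7.7.1), with the first PCR at day 7 (7.5.2).

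**Analysis.** The ITT population includes eligible randomized subjects "regardless of whether they received valganciclovir or had any post-baseline evaluations" (12.3.1). Section 12.5.4 puts all randomized subjects in the denominator and counts deaths and losses without CMV disease as disease-free. It adds an analysis that counts all lost subjects as diseased.

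**Modified ITT.** Section 12.3.2 requires a valganciclovir dose in the prophylaxis arm and a post-randomization PCR in the preemptive arm. Section 12.5.5 excludes preemptive subjects who withdrew before valganciclovir and preemptive subjects without a PCR. It names no prophylaxis exclusion.

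**AE window.** The text of 7.7.4 and 8.1.2 runs AE assessment over the drug period plus 7 days, set individually by viremia treatment in the preemptive arm. The 7.6.1 visit is timed from the last dose.

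**The concern.** Ending follow-up before first dose is nearly neutral when both arms start drug at randomization. Here the pre-drug interval lasts about a day in one arm. In the other it lasts until viremia, and for some subjects it never ends. A preemptive subject taken off study in week 5 without viremia would not be followed; a prophylaxis subject taken off at the same time has been dosed and falls outside the rule.

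The preemptive subject stays in the ITT denominator. Any later CMV disease would go unrecorded and be scored as a success for preemptive therapy, in a trial that also plans a non-inferiority assessment with a 5-point margin.

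The 12.5.5 wording matters because, programmed literally, it analyzes a population other than the one 12.3.2 defines. The AE wording matters because a site with a never-treated subject has no stated stopping date for AE collection and no date for the post-treatment visit.

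**Working it through.** **1. Plan's own figure.** Section 12.1 gives 160 subjects and 20 events for 20% vs 5% at 80% power. By Freedman's log-rank formula, HR = ln(0.95)/ln(0.80) = 0.230. Events = (1.960 + 0.842)² × (1.230/0.770)² = 20.02. Dividing by the mean event rate of 0.125 gives N = 160.1. Exact two-sided Fisher power at 80 per group is 0.793. The sample size reproduces and is not in question.

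**2. Who the rule reaches.** Consent withdrawal before study product has its own paragraph in 5.4.3.3. Ineligible subjects fall outside 12.3.1. Retransplants after day 30 have their own rule in 7.8.2, which applies to both arms. What remains is mainly the investigator's decision to end participation (5.4.3.1). It is unclear whether the ten-day antiviral course after induction counts as study drug: 5.4.2 prescribes it, not 6.2, yet 6.1 admits clinically indicated ganciclovir. If it counts, fewer preemptive subjects are reached.

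**3. Size.** The documents give no number of such leavers, so the fractions below are assumptions.
- n = 88 per arm (176/2).
- f = share of the preemptive arm affected; u = share of their 12-month risk that goes unseen.
- Observed preemptive rate = true rate × (1 − f × u).
- Bias in points at u = 1 is 100 × true rate × f. For f = 1-2% (about 1-2 of 88) this is 0.2-0.4 at a true 20% and 0.05-0.1 at a true 5%.

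Error rates come from full binomial enumeration. Two-sided: unstratified chi-square at 0.05, true rate 20% in both arms. Non-inferiority: one-sided 95% Wald limit against a 5-point margin, true disease 20% prophylaxis vs 25% preemptive.

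| f | Two-sided, u=1 | Two-sided, u=0.5 | Non-inf., u=1 | Non-inf., u=0.5 |
|---|---|---|---|---|
| 0 | 0.0499 | 0.0499 | 0.0517 | 0.0517 |
| 1% | 0.0499 | 0.0499 | 0.0560 | 0.0538 |
| 2% | 0.0502 | 0.0499 | 0.0606 | 0.0560 |
| 5% | 0.0527 | 0.0505 | 0.0763 | 0.0630 |
| 10% | 0.0622 | 0.0527 | 0.1097 | 0.0763 |

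The 5% and 10% rows are an assumed upper bound, not an expectation. All rows assume outcomes are lost in the preemptive arm only. If both arms lose the same proportion (both rates × (1 − f), u = 1), non-inferiority error is 0.0524 at f = 1% and 0.0532 at f = 2%. At 102 per arm (205/2), with preemptive-only loss, f = 1-2% and u = 1, two-sided error is 0.0491-0.0495 (baseline 0.0489) and non-inferiority error 0.0558-0.0608 (baseline 0.0512).

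**4. 12.5.5 against 12.3.2.**
- Preemptive subject with PCR tests who withdrew before valganciclovir: kept by 12.3.2, dropped by 12.5.5.
- Prophylaxis subject never dosed: dropped by 12.3.2, kept by 12.5.5.
- Preemptive subject with no post-randomization PCR: dropped by both.

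**5. AE window.** Several places point to days 1-107 for both arms: the headings of 7.5 (days 1-100) and 7.7.4 (7 days past the treatment phase), section 4 (intervention period of 100 days after randomization) read with 9.5, and the day-107 column in Appendix A. Against this, the text of 7.7.4, 8.1.2 and 7.6.1, the second half of 9.5 and Appendix A footnote 6 refer to drug treatment or last dose. Scheduled safety labs, and with them reporting of ANC below 1000/μL, run through the treatment period with or without drug (7.5.3.1).

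**The case against.** The strongest reply is that the rule has little scope. With the other exits set aside, mainly investigator decision is left, and no figure in the documents supports any particular fraction. That stands, and is why the effect is called probably small.

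The closing sentence of the 5.4.3.3 paragraph can also be read as a specific exception to its opening, and 7.9 is headed as a section on stopping therapy. But the paragraph already names its exception, and the closing clause of 7.9 covers all randomized subjects. The passages still need reconciling.

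Outcome loss may not be one-sided. For dosed subjects who discontinue, 5.4.3.1 promises only that "every effort will be made to complete the safety specific evaluations", so some prophylaxis outcomes could also go unseen unless the opening of 5.4.3.3 governs. The higher non-inferiority figures are therefore a one-arm worst case.

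The plan has safeguards. The lost-as-disease analysis in 12.5.4 and the time-to-event analysis in 12.7.1.1, which censors losses at last follow-up, partly expose the problem. Neither recovers the outcomes, and the primary analysis still scores them as successes.

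On 12.5.5, the formal definition is in 12.3.2, the slip is fairly evident because both clauses name the preemptive arm, and only a supporting analysis is affected. That limits the harm but does not remove the contradiction.

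A reader might infer three stronger things that the documents do not support:
- That never-viremic preemptive subjects in general lose follow-up. The rule applies only to those who discontinue.
- That AEs go uncollected in untreated subjects, so the 12.6.3 comparison is distorted. The headings, section 4 and the Appendix A grid support days 1-107, and 12.6.3 already works per person-day.
- That fewer drug-related events in the preemptive arm would be an artifact. With less drug given, that is a genuine effect of the strategy.

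**Conclusion.** The point holds on three counts of unequal weight.

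(a) The follow-up rule in 5.4.3.3 should be changed. It falls mainly on one arm, conflicts with 5.4.3.3's own opening and with 7.9, and any error it causes through 12.5.4 favors preemptive therapy. At an assumed 1-2% of the arm, two-sided error is essentially unchanged at about 5.0%. Non-inferiority error goes from 5.2% to 5.6-6.1% with loss in the preemptive arm only and all later risk unseen, or to 5.2-5.3% with equal loss in both arms. These figures rest on assumed fractions. The case for change rests on direction and low cost, not on a demonstrated large bias.

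(b) Section 12.5.5 contradicts 12.3.2 and should be corrected before the modified ITT analysis is programmed.

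(c) The AE window and post-treatment visit for never-treated preemptive subjects need only a clarifying statement. On the days 1-107 reading there is no effect on the AE comparison.

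**What to change.** 1. In 5.4.2 and 5.4.3.3, state that every eligible randomized subject is followed to month 12 by record review, whether or not valganciclovir was received, unless consent to data collection is withdrawn, and that replacing a subject does not end follow-up.
2. Reword 12.5.5 to match 12.3.2: exclude prophylaxis subjects with no valganciclovir dose and preemptive subjects with no post-randomization PCR.
3. Reconcile 7.6.1, 7.7.4, 8.1.2, 9.5 and Appendix A footnote 6 so that never-treated preemptive subjects have a stated AE window of days 1-107 and a post-treatment visit at day 107, which Appendix A already lists for all subjects.

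No change is needed to the reportable-event definition in 9.2.3, the person-day comparison in 12.6.3, the halting rules, the sample size or treatment. The cost is protocol wording and a little more abstraction from medical records, which 7.7.3 and 8.1.6 already have staff review at each study visit.
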